2.8.4. Pain assessment

Parents are involved in both the decision of seeking healthcare for musculoskeletal pain and in the discussion with the general practitioner during the clinical encounter ⁵². Therefore, it may occur that data reporting will actually be parent-report rather than child self-report, and this might introduce bias about the pain measurement, especially in longitudinal studies (i.e. children are too young to reliably self-report at the initial assessments, but they might self-report at later follow-up points) ⁵². Current evidence on pain reporting suggest that children are able to self-report from the age of 8 ³⁸, and that the agreement between child and parental report for the presence of pain

is around 50-70%, although the concordance is higher if the pain is of greater intensity and of longer duration ⁵². In addition, when their child's pain is severe, parents might over-report the severity of the impacts of pain on their children as they become more concerned about potential consequences of pain ⁵². Potential inaccuracies in the measurement of knee pain will be considered by means of a question about the persons responding to the follow-up questionnaire (e.g. child alone/parent alone/child together with the parent) as reported in section 2.7.2. Efforts will be done to encourage the same person to respond to all the follow-up questionnaires in order to reduce inaccuracies in pain reporting. For example, a strategy that might be adopted is to provide children with cinema tickets only if they will be the person responding to all the questionnaires.

2.8.5. Study appreciation

Information about study appreciation will be collected by asking participants questions about the acceptability of the questions, acceptability of the time needed for questionnaire completion and the most preferred frequency and method of contact. In addition, evaluation questions about information on the study, the study processes, time required to participate in the study, motivation, future participation to similar studies and potential strategies to implement the study will also be asked to the general practitioners.

2.8.6. Piloting the recruitment procedure and the prognostic tool

This project included a stage where the prognostic tool was piloted, which included a development, testing and implementation stage. Cognitive interviews were carried out after completion of the questionnaires to assess the appropriateness, comprehensibility, wording and

potential lack of items relating to the prognosis of knee pain, as previously done for other tools that evaluated pain status in children and adolescents ^{45,48,49,53}. The aim was to improve the face, construct and content validity of the tool at this stage. This is important especially considering that a worse outcome can result if a general practitioner makes an inaccurate diagnosis of the child's knee pain or if there is a lack of communication between the general practitioner and the child with knee pain ⁵⁴. In addition, children of different age interpret the pain questions differently because of their cognitive development ^{39,40,54,55}. Several self-report measures for pain intensity or the impact of pain exist, with a set of appropriate pain scales for each different age range ^{39,40}, and age-appropriate analogies or metaphors can be used in the knee pain questions in order for the children to understand the questions better ⁵⁴⁻⁵⁶. Therefore, questions as simple as possible were developed in order for the tool to be understandable from individuals of any age ⁴⁵. After this testing and feedback stage, the prognostic tool was implemented and tested again (during a period of 2 months) in an iterative process until reaching the optimal version which will then be used in the data collection stage.

2.8.7. Stability of the prognostic tool study

A pilot study to assess the stability of the prognostic tool (test-retest reliability ⁴⁵) in children pre- and post- consultation was carried out. Children who refer to primary care for knee pain and their parents were given the prognostic tool (together with the informed consent) to be completed in the waiting room of the general practice before the consultation. Subsequently, after the consultation with the general practitioner, children and their parents were asked to complete the prognostic tool again in order to assess the stability of the tool parameters and the general

practitioner's influence on the parameters (e.g. pain perception and psychological factors) assessed with the tool.

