8. Under hver overskrift bedes du sætte kryds i DEN kasse, der bedst beskriver hvordan dine knæsmerter påvirker de ting du laver på en normal dag (f.eks., gå i skole, hobbyer, sport, være sammen med venner eller familie) Hvis du har ondt i begge knæ skal du svare ud fra det knæ hvor smerterne har varet længst	 Jeg har ingen problemer med at udføre mine sædvanlige aktiviteter  Jeg har lidt problemer med at udføre mine sædvanlige aktiviteter  Jeg har nogle problemer med at udføre mine sædvanlige aktiviteter  Jeg har store problemer med at udføre mine sædvanlige aktiviteter  Jeg kan ikke udføre mine sædvanlige aktiviteter
9. Hvor enig er du i dette udsagn "Når jeg har ondt, er det forfærdeligt og jeg tror aldrig det bliver bedre" Sæt kryds i den kasse som bedst beskriver hvordan du har det i dag. Ængstelig/deprimeret svarer til at være ked af det (det handler om hvordan du har det, og ikke nødvendigvis på grund af dine smerter)	 Overhovedet ikke  Lidt  I nogen grad  Meget  Rigtig meget  Jeg er ikke ængstelig eller deprimeret  Jeg er lidt ængstelig eller deprimeret  Jeg er i nogen grad ængstelig eller deprimeret  Jeg er meget ængstelig eller deprimeret  Jeg er ekstremt ængstelig eller deprimeret
10. Har din mor eller stedmor ofte ondt i kroppen? (dette kan både være ondt i hovedet, ryggen, skulderen eller andre steder) Har din far eller stedfar ofte ondt i kroppen? (dette kan både være ondt i hovedet, ryggen, skulderen eller andre steder)	 Nej  Ja  Nej  Ja
11. Hvor mange gange per uge deltager du typisk i sport (udover idræt i skolen)? Hvilken type sport? (feks håndbold, fodbold, svømning, løb). Du må gerne skrive mere end en sport.	 Aldrig  1 gange/uge  2 gange/uge  3 gange/uge  4 gange/uge  5 gange/uge  6 gange/uge  7 eller flere gange/uge (_____)

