2.14. Impact/dissemination

The present study will provide data on the prognosis for knee pain in children and adolescents who present to primary care. In addition, this study will provide data on the usability of a prognostic tool to allocate children and adolescents to a category of risk for knee pain recurrence and consequently provide them with the best targeted treatment. The study results will be disseminated at scientific conferences and through appropriate scientific journals. In addition, general practitioners, children and parents participating into the study will be regularly provided with feedback about the ongoing study.

Examples of papers that might be developed from this study (provisional names are provided):

- 1) The Adolescent Knee Pain (AK-Pain) prognostic tool: protocol for a prospective cohort study
- 2) Stability of prognostic factors for knee pain collected with a questionnaire in general practice
- 3) The development of a prognostic tool for knee pain in children and adolescents in general practice
- 4) Effect on the treatment delivered on the knee pain prognosis on a subsample of the participants recruited in the AK-pain project

3. Protocol amendments

Potential protocol amendments might occur during the prognostic tool piloting and development stage. Protocol amendments will be disseminated to proper scientific journals.

4. Declaration of interest

The study's investigators have no conflicts of interest to declare.

5. Access to data

The final dataset will be accessed by [name], [name], [name] and [name].

References

doi:10.1177/0363546515622456
3. Houghton KM. Review for the generalist: Evaluation of anterior knee pain. *Pediatr Rheumatol.* 2007;5:1-10. doi:10.1186/1546-0096-5-8
5. Rathleff MS. Patellofemoral pain during adolescence: Much more prevalent than appreciated. *Br J Sports Med.* 2016;50(14):831-832. doi:10.1136/bjsports-2016-096328

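### Agreement across a GP consultation is labelled test-retest reliability, which it cannot show for the perception and psychological items or any score containing them

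*Combined protocol and SAP*

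**What the plan says.** Section 2.8.7 presents "A pilot study to assess the stability of the prognostic tool (test-retest reliability") and adds that the comparison "in children pre- and post- consultation was carried out", so the pilot is finished. The first completion was "to be completed in the waiting room of the general practice before the consultation". For the second, "after the consultation with the general practitioner, children and their parents were asked to complete the prognostic tool again". The pair has two stated purposes. One is the stability of the tool's parameters. The other is the GP's "influence on the parameters (e.g. pain perception and psychological factors) assessed with the tool".

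The section gives no sample size, no interval between completions, no agreement statistic and no acceptability threshold. It describes no repeat without an intervening consultation. Section 2.8.6 covers cognitive interviews and iterative re-testing of the tool, and section 2.10 sets out the outcome analyses. Neither contains another reliability assessment.

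Section 2.14 lists a provisional second paper, "Stability of prognostic factors for knee pain collected with a questionnaire in general practice". The tool in section 2.6 mixes factual items (age, sex, smoking in the last four weeks) with items on activity limitation (item 8), catastrophising and mood (item 9, including "Når jeg har ondt, er det forfærdeligt og jeg tror aldrig det bliver bedre") and sleep (item 13).

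**The concern.** Test-retest reliability describes how closely two measurements agree when the underlying state has not changed and the first answers are not simply remembered. Here the event between the measurements is one that the section itself treats as a possible cause of change. A child who has just been reassured, or worried, by a GP may truthfully answer item 9 differently, and the comparison would count that as unreliability. Conversely, a child who remembers the answers just given will agree with them whatever the quality of the item.

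What is at stake is the interpretation of the pilot. High agreement would not show that the perception items are reliable. Low agreement would show neither that they are unreliable nor that the GP changes the answers. The before/after comparison is useful under its proper name, because section 2.8.1 places the baseline questionnaire at the consultation visit without fixing whether it precedes or follows the consultation.

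**Working it through.** The plan states no figure for this pilot, so there is nothing to reproduce. The check is whether one pre/post pair can identify reliability at all. Every variance and shift below is an assumption. A continuous score is used for simplicity, although most items are binary or ordinal.

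**Model.** Pre = T + e1 and Post = T + e2 + d. T is the child's true level, e1 and e2 are response errors with equal variance, and d is the child-specific effect of the consultation, independent of T and of the errors. True reliability = Var(T) / (Var(T) + Var(e)). Observed ICC ≈ Cov(Pre, Post) / mean of the two variances.

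**Check 1: one true reliability, several observed values.** Take Var(T) = 0.75 and Var(e) = 0.25, so true reliability is 0.75.

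- Consultation effect only, Var(d) = 0.25: the covariance is 0.75 and the mean variance is (1.00 + 1.25)/2 = 1.125. ICC = 0.75/1.125 = 0.67.
- Recall only, errors correlated at 0.5: the covariance is 0.75 + 0.5 × 0.25 = 0.875 and the mean variance is 1.00. ICC = 0.875, about 0.88.
- Both: 0.875/1.125 = 0.78.

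The two influences act in opposite directions. In the third case they nearly cancel, but nothing in the design would show that.

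**Check 2: one observed value, several true reliabilities.** Now set Var(T) = 1, with no recall and no mean shift. The variance of the change is 2·Var(e) + Var(d); hold it at 0.5. The two variances then sum to 2 + 0.5 = 2.5, so observed ICC = 2/2.5 = 0.80 however the 0.5 is divided.

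| Share of change variance due to consultation | Var(e) | True reliability | Observed ICC |
|---|---|---|---|
| 0% | 0.2500 | 0.80 | 0.80 |
| 25% | 0.1875 | 0.84 | 0.80 |
| 50% | 0.1250 | 0.89 | 0.80 |
| 75% | 0.0625 | 0.94 | 0.80 |
| 100% | 0 | 1.00 | 0.80 |

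**Check 3: range with a mean shift m.** The agreement ICC is 2·Var(T) / (Var(Pre) + Var(Post) + m²). With Var(T) = 1 and true reliability 0.80, Var(e) = 0.25. With no consultation effect the ICC is 0.80. With an SD of d of 0.7 and m = 0.5 it is 2/(1.25 + 1.74 + 0.25) = 0.62.

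**Could the pair be made to yield the split?** Comparing Var(Post) with Var(Pre) isolates Var(d) only if the error variances are equal and d is independent of T, which one pair cannot verify. The mean shift can be estimated, but it mixes any consultation effect with the effect of simply answering again.

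**The case against.** The strongest reply is that the confounding is disclosed. Section 2.8.7 names the GP's influence as an aim, a before/after comparison suits that aim, and only a parenthetical label for a completed pilot is at issue. This stands as to the design, which needs no defence for the GP-influence aim. It does not rescue the label, because the section offers the same pair as evidence of both properties.

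Several stronger readings are tempting, and the documents do not support them:

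- **That the risk scores or cut-offs rest on this pilot.** They do not. Section 2.10 bases the scoring on logistic regression and the cut-offs on ROC curves, and no step there uses the stability pilot.
- **That paper 2 will claim reliability.** Its provisional title speaks of stability. The concern is that section 2.8.7 treats the two terms as the same.
- **That recall did inflate agreement.** A same-visit repeat is a fair inference from the sequence described, but no interval is given and the size of any recall effect is unknown.
- **That the pilot says nothing about repeatability.** For items a consultation is unlikely to change, agreement can still be read that way, over a short interval if the repeat was within the visit. Age, sex and smoking are the clearest examples. Onset and duration are less safe, since history-taking could prompt a corrected answer.
- **That extra disagreement on items 8, 9 and 13, compared with factual items, measures the consultation effect.** That would require response error to be equal for, say, age and catastrophising, which nothing in the documents supports.

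It is also fair to say that the numerical illustration rests wholly on assumed values and that the documents plan no ICC. The argument about identification does not depend on those values.

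**Conclusion.** The point holds as one of labelling and interpretation. For the perception and psychological items, and any score containing them, agreement across the consultation is neither an estimate of test-retest reliability nor a safe lower bound for it. The documents allow no estimate of the size of the error. Under the assumed variances, a true reliability of 0.75 could appear as about 0.67 to 0.88, and an observed 0.80 is compatible with true values from 0.80 to 1.00 even without recall. The conclusion rests on three things in the text: there is a single pair, the consultation lies between its two members, and no repeat without a consultation is described. The primary and secondary outcome analyses are untouched. The change is worth making because it is cheap and alters what may be concluded from the pilot.

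**What to change.** In section 2.8.7 and in planned paper 2:

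1. Replace the term test-retest reliability with before/after-consultation agreement, and state the interval between completions.
2. Report agreement item by item. Identify items by content as well as number, because section 2.6 says the tool was developed further during piloting and the numbering may have changed.
3. Read agreement as short-interval repeatability only for items the consultation is unlikely to change, most clearly age, sex and smoking.
4. For items it may change, such as activity limitation (8), catastrophising and mood (9) and sleep (13), report agreement and the direction of any mean shift. Describe both as a mixture of response error, re-answering and consultation effect. Do not attribute the excess over the first group to the consultation.
5. State that reliability over an interval without a consultation was not measured.

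The cost is rewording and item-level reporting of data the pilot should already hold; no new data collection is needed. The downside is that the study gives up a reliability claim for the items in step 4 and for any score containing them. Section 2.10 needs no change on this account.

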2.9. Data management and confidentiality

The participant submitted responses will be automatically registered in a database through the Red-cap system (<https://www.project-redcap.org>). Handling of data will comply to the General Data Protection Regulation and the concomitant local data handling instructions for Center of General Practice at Aalborg University. Data will be stored at a server at Aalborg University (a request will be done to store the data for 30 years), this will ensure a safe and legal handling of data. The accuracy of the data will be checked through screening of data outliers and potentially “wrong” or “strange” data will be identified and corrected.

2.10. Analysis plan

The analysis plan that will lead to the development of the final prognostic tool will include the following stages:

1. Descriptive analysis of the collected data. Results will be presented as means with SDs and as percentages.
2. Assessment of potential floor and ceiling effects of the items included in the prognostic tool. This will be done by checking that for those items that represent an ordinal or categorical variable with more than two potential response categories, the responses given are not skewed towards the top or bottom extreme of the scales (e.g. a ceiling or floor effect is present if >15% of the respondents report the lowest/highest score of the scale ^{42,45,57}).
3. Estimation of knee pain prognosis (i.e. recurrence/persistence of knee pain, dichotomous outcome) at 3-month and 6-month follow-up by means of multiple logistic regression to estimate ORs and 95% confidence intervals for each item included in the tool. This will inform on which factors are most related to the prognosis of knee pain and will provide an insight on the scores of the prognostic tool (both overall and for subscales) to be applied for the creation of the initial risk groups. Alternatively, the RR will be estimated if a general linear model analysis will be carried out.
4. Discriminant validity of the prognostic score will be assessed by using receiver operating characteristics (ROC) curves and by calculating the area under the curve (AUC) for the overall score and subscales of the prognostic tool.

[figure not shown]
5. Creation of risk groups for the recurrence/persistence of knee pain on the basis of cut-off scores identified using the ROC curves for the overall tool score. The initial idea is to have three risk groups (low/medium/high), which have to be clinically meaningful. More importance will be given to the sensitivity of the tool over the specificity.
6. Assessment of the predictive ability of the risk groups defined at baseline by calculating the sensitivity, specificity and negative and positive likelihood ratios (LRs) against the primary and secondary outcome (i.e. 3-month and 6-month recurrence/persistence of knee pain; disability/activities limitation due to knee pain).
7. Assessment of the potential influence of non-modifiable patients' characteristics on the predictive ability of the risk groups defined at baseline by stratifying the former analysis by age groups and sex.
8. Calculation of the 3-month and 6-month knee pain prognosis stratified by treatment received and baseline prognostic risk group, provided that data on the treatment given to the patients can be collected. Alternatively, instead of stratifying the analysis by treatment, analysis can be adjusted by treatment received.

In addition, potential changes of the risk groups at 3-month follow-up depending on the treatment received might be calculated provided that the prognostic tool is delivered at the 3-month follow-up as well. In this way it might be possible to track the effectiveness of the treatment and if it resulted in a change of risk group.

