3. Har du ondt i det ene knæ eller begge knæ?	 Kun det ene knæ (højre knæ)  Kun det ene knæ (venstre knæ)  Begge knæ
4. Hvor lang tid har du haft ondt i knæet? Hvis du har ondt i begge knæ skal du svare ud fra det knæ hvor smerterne har varet længst	 under 3 måneder  3–6 måneder  6–12 måneder  mere end 12 måneder (hvor mange år? _____)
5. Hvordan startede dine knæsmerter? Hvis du har ondt i begge knæ skal du svare ud fra det knæ hvor smerterne har varet længst	 Kom pludseligt (f.eks. da jeg fik en skade)  Kom gradvist (f.eks. langsomt over en længere periode)
6. Hvor ofte oplever du dine knæsmerter? Hvis du har ondt i begge knæ skal du svare ud fra det knæ hvor smerterne har varet længst	 Sjældent  Månedligt  Ugentligt  Mere end en gang om ugen  Næsten dagligt
7. Har du ondt andre steder i kroppen som gør at du ikke kan deltage i dine normale aktiviteter (leg i skolegården, sport og lignende)? I dette spørgsmål menes andre steder end knæet	 Nej  Ja. Marker venligst hvor. Du må gerne afkrydse mere end et område:  Hovedet  Ryg eller nakke  Skulder  Albuen  Håndled eller hånden  Underbenet  Låret  Bækkens (badebuksområdet)  Ankel, hælen eller fodden  Andet (_____)

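### The example 15% floor/ceiling limit in step 2 is set for single items, yet an even spread over four or five options already exceeds it, so it flags responses that are not skewed

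*Combined protocol and SAP*

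**What the plan says.** Step 2 of section 2.10 is described as "Assessment of potential floor and ceiling effects of the items included in the prognostic tool". It covers "items that represent an ordinal or categorical variable with more than two potential response categories", so two-option questions are exempt. The aim is to confirm that "the responses given are not skewed towards the top or bottom extreme of the scales". One criterion follows in brackets, introduced as an example and supported by citations: "a ceiling or floor effect is present if >15% of the respondents report the lowest/highest score of the scale".

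The step does not say what happens to a flagged item. It does not apply the limit to the overall or subscale scores, although steps 3 to 5 of the same section work with such scores.

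The questionnaire in section 2.6 shows which items are in scope. They run from item 3 ("Har du ondt i det ene knæ eller begge knæ"), with three unordered answers, and item 4 ("Hvor lang tid har du haft ondt i knæet"), with four ordered answers, to five-option items such as item 8, whose first option is "Jeg har ingen problemer med at udføre mine sædvanlige aktiviteter", and the eight-option sport item 11.

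**The concern.** The more categories a score has, the smaller the share expected in each one. A fixed 15% limit can be informative for a summed score with many possible values. On an item with four or five options, each end category holds more than 15% even when nobody leans towards either extreme. The criterion would then report a floor and a ceiling effect on responses that are not skewed, which is the opposite of what the step sets out to find.

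What is at stake is how step 2 is read. The check is a listed stage on the way to the final tool, and section 2.5 accepts that the number of items may have to fall. A flag that carries little information and has no stated consequence could be cited after the event as a reason to change or drop an item. Nor is a large share at one end of an item in itself a fault in a predictor.

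**Working it through.** **Inputs**

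- Limit: more than 15% of respondents at an end category (section 2.10, step 2). It is a cited convention without a derivation in the plan, so there is no figure to reproduce.
- Options per item, counted from the questionnaire in section 2.6: item 3 has 3 (right, left, both; nominal); item 4 has 4; items 6, 8, 9 first part, 9 second part and 13 have 5 each; item 11 has 8. Item 7 is treated here as a no/yes question with a tick list, so it is out of scope with the other two-option questions.
- Sample sizes: 300 as the main target and 100 as the smaller target from general practice (section 2.5).

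**Step 1: share at each end under an even spread.** With k options this is 1/k.

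**Step 2: what a pass requires.** Both ends must hold at most 15%, so the middle categories must hold at least 100% − 15% − 15% = 70%. An even spread gives them (k − 2)/k.

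| Ordinal items | k | Each end, 1/k | Middle, (k − 2)/k | Above 15%? |
|---|---|---|---|---|
| 4 | 4 | 25% | 50% | yes |
| 6, 8, 9 (both parts), 13 | 5 | 20% | 60% | yes |
| 11 | 8 | 12.5% | 75% | no |

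Six of the seven ordinal items (1 + 5 = 6) exceed the limit when evenly spread. Item 3 is left out of the count because its answers have no order and hence no lowest or highest score.

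**Step 3: chance that an evenly spread item is flagged.** A flag at one end needs a count of at least floor(0.15n) + 1, which is 16 at n = 100 and 46 at n = 300. For one given end this is the binomial tail P(X ≥ 16) or P(X ≥ 46), with X ~ Bin(n, 1/k). For either end it comes from a multinomial simulation with 200,000 draws.

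| k | One given end, n = 100 | One given end, n = 300 | Either end, n = 100 | Either end, n = 300 |
|---|---|---|---|---|
| 4 | 98.9% | about 100% | about 100% | about 100% |
| 5 | 87.2% | 98.4% | 99.2% | about 100% |
| 8 | 18.0% | 8.4% | 33.8% | 16.5% |

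**Step 4: other response shapes.** The plan gives no expected distributions, so these shares are assumptions.

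| Assumed shares (%) | Shape | Flagged, n = 100 | Flagged, n = 300 |
|---|---|---|---|
| 10/25/30/25/10 | symmetric, centre-peaked | 7.8% | 0.5% |
| 11/22/33/22/11 | symmetric, centre-peaked | 16.8% | 3.1% |
| 12.5/37.5/37.5/12.5 | symmetric, four options | 34.0% | 16.5% |
| 13/35/35/15/3 (rounded) | leaning to the low end | 22.0% | 12.9% |

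The last row leans to one side and is flagged far less often than an even five-option item (99.2% at n = 100). On short items the limit responds to how much lies in the middle categories, not to skew.

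**The case against.** The strongest reply is that the 15% is only an example. The operative requirement is the absence of skew, and an analyst could use judgement. That is fair as to how binding the figure is, but it is the only criterion offered, so it is the one likely to be used.

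A second reply is that an even spread is only one kind of unskewed distribution. This stands: symmetric five-option items with a clear central peak usually pass, so it would be wrong to say that the limit can never tell skewed from unskewed responses.

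A third reply is that nothing follows from a flag. Item wording was settled in the pilot (sections 2.6 and 2.8.6), and step 3 estimates an odds ratio for every item with no exclusion for those flagged. This also stands, and it limits the consequence to what step 2 reports. Step 1 already promises percentages, so part of any remedy is in the plan.

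Lastly, the documents alone do not show whether the cited sources confine the 15% convention to total scores. The point does not depend on this. It rests on the number of options in the plan's own questionnaire.

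**Conclusion.** The point holds in a limited form. For six of the seven ordinal multi-category items, the example limit is already exceeded by a perfectly even spread (25% or 20% at each end). The chance of a flag in that case is about 99% or more at 100 participants and about 100% at 300. This contradicts the purpose stated in the same sentence of the plan. The eight-option sport item is below the limit when evenly spread, and the criterion is undefined for item 3. The percentages assume even response shares and the two sample sizes named in section 2.5.

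A reader might infer that step 2 will report a floor or ceiling effect for nearly every item, or that useful predictors will be lost. The documents support neither reading. They give no expected response distributions, two-option items are exempt, centre-peaked items tend to pass, and no step removes or alters a flagged item. No outcome, sample size or model in the plan is shown to change. The criterion is wrong for its purpose as written and cheap to put right.

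**What to change.** Reword step 2 of section 2.10 as follows:

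- Apply the 15% limit to the overall tool score and the subscale scores, which steps 3 to 5 already use.
- For single ordinal items, report the full response distribution and judge skew against the share expected from the number of options (1/k), not against a fixed 15%. The documents give no basis for a particular item-level cut-off. If the team wants one, it should be chosen and justified before the data are seen.
- Leave item 3 out of the check, because its answers have no order.
- State that a flag alone does not remove an item, and that retention rests on the prediction results of step 3.

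The cost is a few lines of wording. The same data are used, no new collection is needed, and the item percentages are already promised in step 1.
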